6.13.7 Clinical Laboratory Adverse Events

The investigator's assessment of each relevant laboratory value will be recorded on the eCRF. For each abnormal laboratory value, the investigator will determine whether the value is considered clinically significant or not. For clinically significant values, the investigator will indicate if the values constitute a new AE and record the sign, symptom, or medical diagnosis on the AE eCRF. The investigator will also record on the AE eCRF

whether the clinically significant values are symptoms or related to previously recorded AEs, are due to pre-existing diseases, or are due to other issues. Adverse events that are grade 3 and 4 will be considered AEs and reported appropriately. The laboratory parameters and the corresponding grading scale are provided in [Appendix 4](#). Additional tests and other evaluations required to establish the significance or aetiology of an abnormal value or to monitor the course of an AE should be obtained when clinically indicated. Any abnormal value that persists should be followed at the discretion of the investigator.

Any seroconversion result for HIV, HAV, HBV, HCV, hepatitis E virus (HEV), or parvovirus B19 (B19V) shall be re-tested.

6.13.8 Serious Adverse Events

6.13.8.1 Definition

An SAE is defined as any AE occurring at any dose that results in any of the following outcomes: death, life-threatening AE, hospitalization, or prolongation of existing hospitalization, a persistent or significant disability/incapacity, or a congenital anomaly/birth defect.

Important medical events that may not result in death, be life-threatening, or require hospitalization may be considered an SAE when, based upon appropriate medical judgment, they may jeopardize the patient and may require medical or surgical intervention to prevent one of the outcomes listed in this definition. Examples of such medical events include allergic bronchospasm requiring intensive treatment in an emergency room or at home, blood dyscrasias, or convulsions that do not result in inpatient hospitalization, or the development of drug dependency or drug abuse.

Moreover, reviewed and confirmed seroconversion for HIV, HAV, HBV, HCV, HEV, or B19V will also be important medical events that shall qualify as an SAE.

6.13.8.2 Reporting Serious Adverse Events

The investigator will report all SAEs to the pharmacovigilance safety desk of the contract research organisation (CRO). The CRO will verify that the applicable laws/requirements for reporting SAEs to the Institutional Review Boards (IRBs)/Ethics Committees (ECs) are followed by the sponsor (Baxter). The sponsor will expedite the SAER forms to the appropriate regulatory authority(ies).

- ALL SAEs ARE TO BE REPORTED TO THE CRO'S SAFETY DESK ON THE SAER FORM WITHIN 24 HOURS AND TRANSMITTED ALONG WITH ANY DE-IDENTIFIED SUPPORTING DOCUMENTATION IN THE ENGLISH LANGUAGE TO THE SPONSOR WITHIN 24 HOURS OF BECOMING AWARE OF THE EVENT

**See SAER form for contact information.
Further details are also available in the study team roster.**

For definitions and information on the assessment of these events, refer to the following:

- Section 6.13, Adverse Events Assessments
- Section 6.13.1, Performing Adverse Events Assessments
- Section 6.13.8, Serious Adverse Events

6.13.9 Urgent Safety Measures

An urgent safety measure is an immediate action taken, which is not defined by the protocol, in order to protect patients participating in a clinical trial from immediate harm. Urgent safety measures may be taken by the sponsor or clinical investigator, and may include any of the following:

- Immediate change in study design or study procedures
- Temporary or permanent halt of a given clinical trial or trials
- Any other immediate action taken in order to protect clinical trial participants from immediate hazard to their health and safety.

The investigator may take appropriate urgent safety measures in order to protect patients against any immediate hazard to their health or safety. The measures should be taken immediately and may be taken without prior authorisation from the sponsor. In the event(s) of an apparent immediate hazard to the patient, the investigator will notify the sponsor immediately by phone and confirm notification to the sponsor in writing as soon as possible, but within 1 calendar day after the change is implemented. The investigator will also ensure the responsible IRB/EC and national competent authority (NCA) is notified of the urgent measures taken in such cases according to local regulations. The CRO should verify that the responsible IRB/EC and the sponsor (Baxter) have been informed of the event in an expedited manner as stated above.

6.13.10 Untoward Medical Occurrences

Untoward medical occurrences occurring before the first exposure to IP/control are not considered AEs; however, each serious untoward medical occurrence experienced before the first IP/control exposure (ie, from the time of signed ICF up to but not including the first IP/control exposure) will be described on the SAER form.

6.13.11 Treatment-emergent Adverse Events

A treatment-emergent AE is defined as any AE that occurs after the onset of study treatment administration through the end of the study.

6.14 Concomitant Medication Assessments

Ongoing prior medications will be recorded as concomitant medication once the study treatment has been initiated. During treatment, concomitant medications and therapies (including dose, frequency, start and stop dates, and indication for use), will be recorded in the eCRF by study site personnel on a daily basis.

6.15 Non-Medical Complaints

A non-medical complaint (NMC) is any alleged product deficiency that relates to identity, quality, durability, reliability, safety, and performance of the product but does not result in an AE. Non-medical complaints include but are not limited to the following:

- A failure of a product to exhibit its expected pharmacological activity and/or design function (eg, reconstitution difficulty).
- Missing components.
- Damage to the product or unit carton.
- A mislabelled product (eg, potential counterfeiting/tampering).
- A bacteriological, chemical, or physical change or deterioration of the product causing it to malfunction or to present a hazard or fail to meet label claims.

Any NMCs of the product will be documented on an NMC form and reported to the sponsor within 1 business day. If requested, the defective product(s) will be returned to the sponsor for inspection and analysis according to procedures.

6.16 Removal of Patients from the Trial or Study Drug

A patient is considered to have completed the study when he/she ceases active participation in the study because the patient has, or is presumed to have, completed all

study procedures according with the protocol (with or without protocol deviations). Any other cases are classified as discontinuation.

Reasons for completion/discontinuation will be reported on the Completion/Discontinuation eCRF, including: Completed, AE (eg, death), discontinuation by patient (eg, lost to follow-up [defined as 3 documented unsuccessful attempts to contact the patient], dropout), physician decision (eg, pregnancy, progressive disease, protocol violation[s], recovery), study terminated by sponsor, or other (reason to be specified by the investigator [eg, technical problems]). Screening failures will be recorded on the Screening Failures form. Regardless of the reason, all data available for the patient up to the time of completion/discontinuation should be recorded on the appropriate eCRF.

Every effort will be made to have discontinued patients complete the study completion/termination visit. If the completion/termination visit is done as an additional, unscheduled visit, the assessment results shall be recorded with the completion/termination visit. If a patient terminates participation in the study and does not return for the completion/termination visit, his/her last recorded assessments shall remain recorded with his/her last visit. The reason for discontinuation will be recorded and the data collected up to the time of discontinuation will be used in the analysis and included in the clinical study report. If additional assessments are required, the assessments shall be recorded separately. Assessments to be performed at the termination visit (including cases of withdraw or discontinuation) can be found in [Appendix 2](#) (Schedule of Study Procedures and Assessments) and [Appendix 4](#) (Clinical Laboratory Assessments).

In the event of patient discontinuation due to an AE, clinical and/or laboratory investigations that are beyond the scope of the required study observations/assessments may be performed as part of the evaluation of the event. These investigations will take place under the direction of the investigator in consultation with the sponsor, and the details of the outcome may be reported to the appropriate regulatory authorities by the sponsor.

6.17 Appropriateness of Measurements

Measurements to be performed during the course of the study (with the following exceptions) are standard for the indication or patient population under study:

- The Valsalva manoeuvre, while not standard, is necessary to assess intra-operative CSF leakage that may not be easily identified on visual inspection.
-
- 

7. STUDY ACTIVITIES

7.1 Screening and Study Visits

The study site is responsible for maintaining an enrolment/screening log that includes all patients enrolled. The log will also serve to document the reason for screening failure.

The overall study design is illustrated in [Appendix 1](#). Details on the procedures to be performed at each study visit, including screening, can be found in [Appendix 2](#) (Schedule of Study Procedures and Assessments) and [Appendix 4](#) (Clinical Laboratory Assessments).

7.2 Pre-operative Screening Visit (Days -30 to -1)

- Obtain IC.
- During the pre-operative screening visit, the investigator will determine if the patient meets all pre-operative inclusion criteria and none of the pre-operative exclusion criteria.
- Record demographics (including weight, height, and body mass index), medical history, physical examination results, an assessment of neurological status, vital signs, and ECG results.
- Measure baseline clinical laboratory values (see [Appendix 4](#)).
- Record AEs.
- Record concomitant medications and non-drug therapies.

7.3 Procedures for Day 0 Treatment (Pre-operative)

- Re-assess patient to confirm that the patient is ready for surgery and meets the pre-operative inclusion criteria and none of the exclusion criteria. No changes in health status have occurred between the initial screening and the day of surgery that would affect the patient and/or study conduct.
 - Record medical history, physical examination results, an assessment of neurological status, vital signs, and weight.
 - Perform a urine screening for pregnancy test (for women of childbearing potential). If screening occurred more than 48 hours prior to performing the operation, baseline clinical laboratory values (see [Appendix 4](#)) will be measured.
 - Record AEs.
-
- 

- Record concomitant medications and non-drug therapies.
- Perform pre-operative randomisation (surgeon remains blinded to treatment until intra-operative screening is complete, as described in Section 7.4)

7.4 Procedures for Day 0 Treatment (During and After Surgery)

- Perform intra-operative screening for inclusion and exclusion criteria and a check for CSF leak after placing primary suture.
 - Randomised treatment is revealed to the surgeon
 - Apply IP or control treatment to the CSF leak site.
 - Administer peri-operative antibiotic.
 - Collect the following surgery details:
 - Start (skin cut),
 - Start (application of IP/control),
 - End (last skin suture),
 - Length of sutured durotomy (cm),
 - Surgical complications,
 - Suture type used for dura closure (brand, type, size),
 - Suture closure technique (eg, continuous simple, continuous locked, interrupted),
 - Use of autologous or non-autologous dural material,
 - Use of tenting sutures (Yes/No),
 - Rescue therapy (Yes/No, if Yes: reason, brand, type, technique).
 - Assess primary endpoint part 1: check for CSF leakage (Yes/No) after up to two IP/control applications during the Valsalva manoeuvre (up to 25 cm H₂O for up to 5 - 10 seconds). Any visible CSF is considered positive for CSF leak.
 - Post-operatively, monitor vital signs and perform physical examination, neurological assessment, and ECG.
-
- 

7.5 Procedures for Day 5 (± 2 Days) or the Day Before Discharge (Whichever Comes First), and Day 30 (± 3 Days)

- Record physical examination results, an assessment of neurological status, vital signs, ECG, and weight.
- Measure clinical laboratory values (see [Appendix 4](#)).
- Assess primary endpoint part 2: check for CSF leakage.
- Assess surgical site.
- Document any need for surgical revision.
- Check drain duration and output, if present.
- Document the number of unplanned interventions.
- Record AEs.
- Record concomitant medications and non-drug therapies.

7.6 Procedures for Day 60 (± 3 Days) and/or Study Completion

- Record physical examination results, an assessment of neurological status, vital signs, ECG, and weight.
- Measure clinical laboratory values (see [Appendix 4](#)).
- Perform assessment of CSF leak.
- Assess surgical site.
- Document any need for surgical revision.
- Document length of stay and number of days in the intensive care unit (ICU).
- Document the number of unplanned interventions.
- Record AEs.
- Record concomitant medications and non-drug therapies.

7.7 Procedures for Unscheduled Follow-up (Between Days 5 [± 2] to 60 [± 3])

- Record physical examination results, an assessment of neurological status, and vital signs.
 - Measure clinical laboratory values (see [Appendix 4](#)).
 - Perform assessment of CSF leak.
 - Assess surgical site.
-
- 

- Document any need for surgical revision.
- Record AEs.
- Record concomitant medications and non-drug therapies.

8. QUALITY CONTROL AND ASSURANCE

8.1 Auditing

The sponsor and/or sponsor's representatives may conduct audits to evaluate study conduct and compliance with the protocol, standard operating procedures, other written instructions/agreements, International Conference on Harmonisation (ICH) Good Clinical Practice (GCP), the IRB/IEC and applicable regulatory guidelines/requirements. The investigator will permit auditors to visit the study site, as described in the Clinical Study Agreement. Auditing processes specific to the study will be described in the auditing plan.

8.2 Non-compliance with the Protocol

The investigator may deviate from the protocol only to eliminate an apparent immediate hazard to the patient. In the event(s) of an apparent immediate hazard to the patient, the investigator will notify the CRO immediately by phone and will confirm notification to the CRO in writing as soon as possible, but within 1 calendar day after the change is implemented. The investigator will also ensure the responsible IRB/EC/NCA is notified of the urgent measures taken in such cases according to local regulations.

If monitoring and/or auditing identify serious and/or persistent non-compliance with the protocol, the CRO may terminate the investigator's participation. The CRO will notify the IRB/EC and applicable regulatory authorities of any investigator termination.

9. PLANNED STATISTICAL METHODS

9.1 General Considerations

The Statistical Analysis Plan (SAP) is a separate document that will provide a more technical and detailed elaboration of the principal features stated in the protocol. Any deviations from the planned analyses will be described and justified in the final clinical trial report.

9.2 Determination of Sample Size

This study is designed to show non-inferiority (NI) of FS VH S/D 500 s-apr compared to DuraSeal Dural Sealant based on the primary composite efficacy endpoint. The proportion of patients meeting the composite primary endpoint is assumed to be █% for FS VH S/D 500 s-apr and █% for DuraSeal. Using a non-inferiority margin of 10% (the largest clinically acceptable difference), a 1-sided Type 1 error rate (α) of 2.5%, a statistical power ($1-\beta$) of 80%, that one interim analysis is performed after 50% of the patients complete the study, the sample size estimation results in 202 evaluable patients. Assuming a group sequential design utilising O'Brien-Fleming boundaries, the study may be stopped early for futility if a p-value >0.2486 is observed at the interim. The estimation of sample size was performed using █ software (█, █).

The primary analysis will be performed on the per protocol set (PPS). Assuming that the PPS is 10% less than the total number of randomised patients, 112 patients per treatment group should be randomised, and there will be 224 patients in total.

9.2.1 Justification of Non-Inferiority Margin

The 10% NI margin is mainly based on literature review, the screening of multiple key opinion leaders (clinical judgment), and a previous clinical study for a comparable product that led to biologic license application (BLA) approval.

- Literature review (Weber 2012)⁸: In a retrospective analysis of 1395 cranial surgeries, post-operative CSF leaks occur in approximately 7.7%, across all types of cranial surgeries. However, tight dural sutures by inspection were followed by CSF leaks in 4.7%. Tight suturing of the dura mater with additional securing and/or augmentation of the suture by a different technique (covering with muscle or fascia flab, gelitta, fibrin glue, hydrogel gel, or others) is performed 68% of the time. The subgroups with different dural closure augmentation techniques
-
- █

- (fleece-bound sealant, glue, dural-plasties, etc.) were too small to detect any statistically demonstrable effect on CSF leaks after cranial surgery.
- Clinical judgment: Based upon discussion with clinicians (neurosurgeons) on the use of dural sealants as an adjunct to suture line, the consensus was that NI could be claimed if the maximum difference of success rate (ie, CSF leakage free) between the new treatment (Tisseel) and the current treatment (DuraSeal) is 10%, with the assumption that the proportion of patients meeting the composite primary endpoint is at least 85.0% for DuraSeal.
 - Previous clinical study: A 10% NI margin was used in a previous Phase III pivotal, NI study. In this study, a new dural sealant (Adherus) was compared to the same control (DuraSeal) and the study design including patient population, eligibility criteria, and the primary endpoint was very similar to the current Tisseel study.²⁹ Thus, the assumed proportion of 90.6% for DuraSeal in the current Tisseel study is based on results of this previous study evaluating Adherus and DuraSeal.

9.3 Analysis Populations

9.3.1 Full Analysis Set (FAS)

The patients who were randomised and treated with at least 1 dose of IP/control will be included in the Full Analysis Set (FAS).

9.3.2 Per Protocol Set (PPS)

The patients included in the FAS without any major protocol deviations, which could impact the primary endpoint assessment, will be included in the Per Protocol Set (PPS). The PPS is defined by the following:

- Patients who meet all inclusion criteria and do not meet any exclusion criteria.
 - Patients who are randomised and treated according to the randomisation scheme.
 - Patients with no major protocol deviations which could impact the primary endpoint assessment.
 - Availability of primary endpoint assessment.
-
- 

Furthermore, any other major protocol violations, such as serious unforeseen violations deemed to invalidate the data and affect the conclusions of the study, will lead to the exclusion of patients from the PPS.

9.3.3 Safety Analysis Set

The patients who received at least 1 dose of IP/control will be included in the Safety Analysis Set. Patients will be analysed as treated (in case of incorrect randomisations).

9.4 Methods of Analysis

The efficacy endpoints will be analysed for the FAS and the PPS, with the PPS being considered as primary and the FAS as supportive.

The safety endpoints will be analysed for the safety data using the safety analysis set.

Categorical data will be summarised using frequencies and percentages, while continuous data will be presented using descriptive summary statistics (the number of patients [N], mean, standard deviation, median, minimum, and maximum).

No imputation of missing data will be performed, unless otherwise specified.

All efficacy and safety endpoints will be listed in patient data listings.

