9.4.2 Primary Efficacy Endpoint

The primary efficacy endpoint is the proportion of patients who have neither of the following:

- Intra-operative CSF leakage from dural repair after up to two FS VH S/D 500 s-apr/control applications during Valsalva manoeuvre (25 cm H₂O for up to 5 - 10 seconds)
- Post-operative CSF leakage within 30 (+3) days post-operatively

The specific hypotheses of the proportion difference to be tested are as follows:

$$H_0: P_{FS} - P_{DS} \leq -0.10$$

$H_a: P_{FS} - P_{DS} > -0.10$

where

P_{FS} = the proportion of patients not meeting the 2 criteria (ie, no intra-operative CSF leakage and no post-operative CSF leakage) for the FS VH S/D 500 s-apr treatment group, and

P_{DS} = the proportion of patients not meeting the 2 criteria (ie, no intra-operative CSF leakage and no post-operative CSF leakage) for the DuraSeal Dural Sealant treatment group.

The primary composite efficacy endpoint, proportion of patients not meeting the 2 criteria (ie, no intra-operative CSF leakage and no post-operative CSF leakage), will be investigated by a 2-sided test for non-inferiority using logistic regression, taking into account the following covariates: study center and surgery region. Non-inferiority of FS VH S/D 500 s-apr to DuraSeal Dural Sealant will be assessed using the confidence interval approach and a NI margin of 10%.

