9.4.3 Secondary Efficacy Endpoints

The secondary efficacy endpoints are the following:

- Incidence of intra-operative CSF leakage following final Valsalva manoeuver
- Incidence of CSF leaks within 30 (+3) days post-operatively
- Time in surgery (minutes)
- Time from dural closure (application of IP) until end of surgery
- Length of stay in hospital (days)

The logistic regression approach used for the primary efficacy endpoint will also be used to calculate the proportions of patients with incidence of intra-operative CSF leakage following final Valsalva manoeuver and incidence of CSF leaks within 30 (+3) days post-operatively.

The time in surgery, time from dural closure until end of surgery, and the length of stay in hospital will be compared between the 2 groups using a Wilcoxon rank sum test.

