^g Surgery details to be captured: start (skin cut), start (application of IP/control), end (last skin suture), length of sutured durotomy (cm), surgical complications, suture type used for dura closure (brand, type, size), suture closure technique (continuous simple, continuous locked, interrupted), use of autologous or non-autologous dural material, use of tenting sutures (Y/N), rescue therapy (Y/N, brand, type, technique).

^h CSF leakage will be assessed after up to two IP/control applications during the Valsalva manoeuvre (up to 25 cm H₂O for up to 5 – 10 seconds).

ⁱ Days in hospital (Day 0 - Discharge).

^j Re-do surgery details to include: indication, type, complications.

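### The per-protocol set leads for three secondary tests of a difference, where the full analysis set would be better protected against selection at almost no cost

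*Protocol*

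**What the plan says.** Protocol 9.4 covers the efficacy endpoints together: "The efficacy endpoints will be analysed for the FAS and the PPS, with the PPS being considered as primary and the FAS as supportive". It makes no exception for secondary endpoints.

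The two sets differ in how patients enter them:

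- **FAS (Protocol 9.3.1):** "The patients who were randomised and treated with at least 1 dose of IP/control will be included in the Full Analysis Set". Nothing is required of the endpoint data. SAP 6.2 adds that patients are analysed in the arm to which they were randomised.
- **PPS (Protocol 9.3.2):** FAS patients who met eligibility, were treated as assigned, had no major deviation bearing on the primary endpoint, and satisfy "Availability of primary endpoint assessment". The primary endpoint (Protocol 9.4.2) includes "Post-operative CSF leakage within 30 (+3) days post-operatively".
- **PPS (SAP 6.3):** the exclusion list names improper assessment of the primary endpoint, but not a missing one.

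Protocol 9.4.3 lists five secondary efficacy endpoints. Two are leak incidences, handled by the logistic model of the primary analysis. The other three are time in surgery, time from dural closure to end of surgery, and length of stay, which "will be compared between the 2 groups using a Wilcoxon rank sum test". SAP 10.2 repeats these methods and names no analysis set. SAP 6.2 and 10.1 attach the PPS to the primary efficacy analysis. SAP 13.1 plans the secondary efficacy tables on both sets (14.2.2.1 for the PPS, 14.2.2.2 for the FAS).

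**The concern.** The usual reason for leading with a PPS in a non-inferiority trial is that deviations and cross-over can blur a true difference, and blurring favours a non-inferiority claim. The three Wilcoxon endpoints have no margin and no non-inferiority hypothesis. For a test of a difference, that argument gives no reason to prefer a set chosen after randomisation, and the as-randomised set is the better protected one.

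Selection is a realistic worry here. SAP 6.3 removes patients for treatment errors and improper administration of study product, events that could themselves accompany a longer operation. It settles deviations at a data review meeting, while Protocol 5.6 leaves site, contract research organisation and sponsor staff unblinded. The two products also have different application steps (Protocol 6.9.1 and 6.9.2), so deviations need not fall equally on the arms.

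The endpoint-availability condition is also unrelated to these outcomes. Leak status to Day 30 has no bearing on whether a surgery time is known. At stake is which result leads if the two sets disagree, together with a small loss of precision.

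**Working it through.** **1. When each value is fixed, against what PPS entry requires**

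| Endpoint | Value fixed | Source | Needs Day 30 leak status? |
|---|---|---|---|
| Time in surgery | Day 0 | Protocol 7.4 (first skin cut, last skin suture) | No |
| Time from dural closure to end of surgery | Day 0 | Protocol 7.4, "Start (application of IP/control" and last skin suture | No |
| Length of stay | Discharge | Protocol Appendix 2, "Days in hospital (Day 0 - Discharge" | No |
| Composite primary endpoint | Up to Day 30 (+3) | Protocol 9.4.2 | Yes, if watertight in surgery |

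A patient who was watertight in surgery and lost before Day 30 has both surgery times but no primary endpoint. Protocol 9.3.2 puts that patient outside the PPS.

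Two limits apply. A patient with an intra-operative leak is already a failure (Protocol 6.10), so a missing Day 30 status need not make the endpoint unavailable; the documents do not say how this case is classified. And although length of stay is fixed at discharge, Protocol 7.6 and Appendix 2 schedule its documentation at Day 60 or study completion, so it may be missing too for a patient lost early.

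**2. The plan's own allowance**

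Inputs (Protocol 9.2): 202 evaluable patients, PPS 10% smaller than the randomised number, 112 per arm.

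- 202 / 0.90 = 224.4, which rounds up to 225. The plan states 224.
- In reverse, 224 × 0.90 = 201.6, about 202. The plan's figure is reproduced to within rounding.
- Difference: 224 − 202 = 22 patients, about 11 per arm. This counts PPS exclusions for every reason; the share due to missing Day 30 status is not given.

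**3. Precision**

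The standard error of a two-arm comparison varies as 1/√n per arm:

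SE(PPS) / SE(FAS) = √(112/101) = 1.053, about 5% larger.

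**4. Power at assumed effects**

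No effect size or power is stated for these endpoints, so standardised differences d are assumed. Approximate two-sided 5% Wilcoxon power uses the efficiency factor 0.955 (normal data):

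power = Φ( d × √(0.955 n / 2) − 1.96 )

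For d = 0.3 and n = 101: 0.3 × √48.23 − 1.96 = 0.123, and Φ = 0.549. The other entries follow in the same way.

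| Assumed d | PPS, 101 per arm | FAS, 112 per arm | Loss (points) |
|---|---|---|---|
| 0.3 | 54.9% | 59.2% | 4.3 |
| 0.4 | 79.3% | 83.3% | 4.0 |
| 0.5 | 93.5% | 95.5% | 2.0 |

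This assumes that all 112 per arm have a value, so it is the most that the FAS could recover under the 10% allowance.

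**5. Bias**

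Its size and direction depend on who is excluded, in which arm, and how their times compare with the rest. The documents give none of these, so no figure is offered.

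**The case against.** The strongest reply is that little turns on the label. Protocol 9.4 requires both sets, both tables are planned, and no power, testing order or claim is attached to the three endpoints. That stands as to size. It does not settle which result leads if the sets disagree, and on that Protocol 9.4 is explicit.

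A second reply is that under the SAP the Day 30 example may not arise, because SAP 6.3 does not list a missing primary endpoint as an exclusion and SAP 7.2 deals with missing values by availability of endpoint data. This is correct on the SAP's text and exposes a mismatch with Protocol 9.3.2. It does not remove the point. Protocol Amendment 2 (06 Nov 2017) is later than SAP version 2.0 (10 Aug 2017), SAP 10.2 names no set that would override Protocol 9.4, and exclusion for deviations after randomisation remains under both documents.

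A reader might also infer three stronger things that the documents do not support:

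- **That the data are discarded.** They are not. The supportive FAS run keeps every treated patient with a recorded value.
- **That the plan contradicts itself by analysing a fourth Wilcoxon endpoint, unplanned interventions, on all treated patients.** That endpoint is classed as safety (Protocol 9.4.4), and the safety set is analysed as treated. It is no precedent for an as-randomised efficacy analysis.
- **That 10% of patients drop out because Day 30 is missing.** The 10% is a planning allowance for all PPS exclusions.

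**Conclusion.** The point holds as a modest improvement. Protocol 9.4 applies a non-inferiority rationale to three tests of a difference, so their lead result comes from a set selected after randomisation and, under Protocol 9.3.2, partly by an unrelated endpoint's availability.

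If PPS exclusions reach the planned 10% and the FAS values are complete, the cost is a standard error about 5% larger and about 2 to 4 points of power at standardised differences of 0.3 to 0.5. Both are upper figures under that allowance: for length of stay the FAS may recover less, given when it is documented. It is tempting to quote a fall from 80% to 76% power, Φ(2.80 × √(202/224) − 1.96) = 0.758. The arithmetic is right, but the 80% belongs to the primary test; no secondary endpoint was given a power.

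The better reason for change is protection against selection, which cannot be quantified here. The composite non-inferiority conclusion and the sample size are not affected.

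**What to change.** In Protocol 9.4 and SAP 6.2 and 10.2, name the analysis set for each efficacy endpoint:

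- **Composite non-inferiority test and the two secondary leak endpoints:** PPS primary, FAS supportive, as Protocol 9.4 has it now. Naming the leak endpoints avoids leaving them without a lead set.
- **Time in surgery, time from dural closure to end of surgery, length of stay:** FAS, as randomised, primary; PPS supportive.

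Align Protocol 9.3.2 and SAP 6.3 on whether a missing primary endpoint excludes a patient from the PPS, and say how a patient with an intra-operative leak and no Day 30 status is classified.

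The cost is a few sentences. Tables 14.2.2.1 and 14.2.2.2 are already planned, so no new patients, data or outputs are needed. The change should be made before results by arm are seen.
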